
**Specific Aim #1: Using focus groups, identify VA enrolled OEF/OIF/OND RNG female war Veterans' perceptions, preferences and identified barriers and facilitators to accessing VA MH services and EBP (including cognitive processing therapies and prolonged exposure therapy) for PTSD.**

Hypothesis 1.a: OEF/OIF/OND RNG servicewomen with PTSD who differ in factors associated with access to care based on Aday and Andersen's (1974) model will identify different barriers and facilitators to VHA services for PTSD including EBP.

Hypothesis 1.b: With improved understanding of the consumer's perceptions of, or experiences with VA mental health care for PTSD and EBP, we can further tailor our existing web-based educational interface to better address the gap between PTSD care need and EBP access.

**Specific Aim # 2: To evaluate the participants' perceptions of and satisfaction with the revised web-based interface and to evaluate and test differences in VHA initiation and use for those who screen positive for PTSD by randomly assigned route: 1) Study concierge nurse case manager (NCM) or 2) existing outreach.**

Hypothesis 2.a: Web-based interface is a successful way to improve Veterans' post-deployment health education and VA access as demonstrated by web-intervention satisfaction survey and subsequent enrollment.

Hypothesis 2.b: Use of a nurse case manager to promote shared decision-making regarding PTSD services and EBPs will result in increased use of MH care and initiation of EBP for PTSD compared to outreach counselors.

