## Phase 2:

Phase 2 of the study will involve 5 Steps: 1) Web-based pre-interface survey; 2) web-based screening and tailored education and resource links; 3) post-interface satisfaction and intended care survey; 4) random assignment to concierge nurse case manager versus in place OEF/OIF/OND outreach workers 5) post-intervention follow-up.

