Phase 2 Intervention Process: The web-based interface provides online screening scores and individually tailored educational and referral information to participants (see appendix for current version). Following IRB approval, potential subjects will receive a postal mail invitation and information summary. This will be followed within the same week by an e-mail summary of the project and invitation to complete an online tailored questionnaire that will be administered using software developed by Pharos Innovations Corporation. In the email, potential subjects will be provided with an embedded web link and a subject identification number that can be used to access the online survey/educational interface. A consent document will be included in the initial survey screens prior to beginning the survey. The survey and responses will be maintained on a secure server behind the VA firewall. The web-based pre-screening survey will query prior and current VA utilization and their reasons for accessing it or not, knowledge about post-deployment VA eligibility and services and satisfaction with VA care, a brief check list of barriers and facilitators to VA MH care and to EBP (gathered from focus group information), and non-VA MH service use.

The web-based screens will include the following:

1. PTSD - VA Post-Traumatic Stress Disorder (PTSD) Screen
2. Sexual Trauma - VA Military Sexual Trauma Screen
3. Combat Exposure - Exposures to Combat Screen (Hoge et al (2009))
4. Domestic Violence - American College of Obstetrician and Gynecologist domestic violence screen
5. Family Readjustment- developed from PI's focus groups from another HSR&D funded study
6. Substance Abuse - AUDIT-C Substance Abuse Screen (VA screen)
7. Prescription Drug Abuse- DoD Survey of Health Related Behaviors modified for web
8. TBI - VA Traumatic Brain Injury (TBI) Screen, modified to include more descriptive questions
9. Depression - Physician's Health Questionnaire (PHQ-9) depression questions

Even though the focus of this study is on PTSD, these additional screens are necessary because of frequent comorbidities with PTSD and also to inform the NCM regarding the comorbid conditions. In our preliminary study of this web-interface, most participants completed the screening and education on the same day (92%). Those who did finish the interview on the same day had an average completion time of 26 minutes (median of 17 minutes), ranging from 8 to 221 minutes.

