All contact professionals and PBRN/CREATE sites will be involved prior to study initiation, educated about this study, and engaged in facilitating outreach and care. It is noteworthy that our research team's studies that use focus groups and telephone interviews with more intensive questions about sexual assault in RNG populations have not resulted in any subsequent clinical emergencies. Women who have no positive screens will be able to access the same educational information and web links if they choose to. The web-based post-screening survey immediately following the screening and education interface will be revised from our original web-and semi-structured survey to include satisfaction with information about VA MH and EBP for PTSD that they receive in the web education intervention. We will also repeat the check-list of barriers and facilitators to VA MH care and to PTSD EBP tailored from the participant's prior responses to determine if the web-based intervention altered their perceptions. We will also query those who are PTSD positive and who are not engaged in PTSD EBP and other MH care whether they intend to seek care as a result of their participation and why or why not. Participants will be reimbursed \$30.00 for the time and effort to complete the web-interface and pre-and post-surveys. If they complete the web-interface and pre and post surveys within two weeks following their initial postal or e-mail invitation then they will receive an additional \$10.00. In order to receive subject reimbursement, participants will be asked to provide their names and social security number to the coordinator through a toll-free number. These data and linkage study ID number will be maintained in a locked and limited access research network electronic file behind the VA firewall. With these subject identifiers we are able to access participant VA records, given subject IRB consent. VA health services utilization will be obtained from all consenting participants in this phase of the study, including initiation of mental health services (either in primary care or specialty care) and extent of participation in EBP. Participation will be measured by self-report of EBP engagement, type, and number of sessions. This will be validated by VA electronic chart review.

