**Random Assignment to Route of VA PTSD EBP Access:** As indicated in their IRB informed consent document for study Phase 2, RNG women Veterans who screen positive for PTSD will be randomly assigned by the web interface to one of two conditions: 1) a study-specific nurse NCM using shared decision-making to assist with

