local VA mental health and PTSD evaluation and treatment in the Veteran's locale, or 2) OEF/OIF/OND outreach coordinators in place at every VA. A toll-free number will be provided to participants assigned to the NCM with information that they can initiate contact and that they otherwise will be telephoned by the NCM within 2 weeks following completion of the post-intervention survey. Pharos Innovations (web-interface developer) will provide immediate notification to the study NCM of participants who are assigned to each group and she will be able to access web results of participant study screens. Upon telephone contact with the participant, the concierge NCM will engage the patient and by telephone administer a 17 item PTSD Checklist (PCL) developed by the National Center for PTSD to assess the presence of DSM-IV criteria for PTSD. She will use the PCL-S that allows identification of a specific traumatic event. This will assist with PTSD validation and allow for individualized referral. The NCM will then follow shared decision making protocols for specific domains (Joosten et al., 2008). Domains include (pending focus group augmentation): 1) Actively reporting all information and PTSD treatment possibilities to the patient/consumer. The NCM can recommend an option but PTSD treatment and therapy are decided jointly; 2) Encourages the patient to discuss preferences and form their own judgment regarding the harms and benefits of PTSD treatment/EBP options; 3) Makes sure that the information exchange is two-way between patient and NCM; 4) NCM informs partner or key family members who the Veteran includes in the telephone interface in the PTSD treatment decision-making process; 5) Informs Veteran about routes of access to VA or if already enrolled ways to access PTSD EBP and facilitates as needed and actively links with care; and 6) Addresses barriers and facilitators checked by the Veteran on her web-based interface and assists the Veteran in addressing these (e.g., education regarding night clinics, transportation). The NCM will review all PTSD treatment options, including pharmacotherapy and site specific options, e.g. unique groups. Subjects will be educated about the efficacy, risks and benefits, duration of each treatment option. Participants are welcome to re-contact the NCM on our toll free number for further questions and assistance with care initiation or transitions during the duration of the study. However, the NCM will not initiate further follow-up. The study concierge NCM, [name], R.N., M.S. will build on her own skills as a career Army nurse and prior OEF/OIF outreach counselor. She will be trained in the intervention protocol by PI ([name]) and co-I (MV) who are MH care professionals with unique clinical and research expertise specific to this intervention. NCM model fidelity and tools developed (manual, check lists for PTSD and MH utilization, satisfaction) will be guided by consultant [name], who has expertise specifically useful to this with his work with the VA's Translating Initiatives for Depression into Effective Solutions (TIDES) project in his QUERI implementation expert role. It should be noted that the NCM will use VA/DoD Clinical Practice Guidelines for The Management of PTSD (<http://www.healthquality.vagov>) for assistance with patient education, management, and tracking utilization specific to EBP but also other PTSD treatment interventions documented on the treatment checklist tracking utilization in post-intervention follow-up. Use of PBRN and CREATE study sites will allow NCM interface with PC, WHC, and MH teams already sophisticated about and engaged in evolving women's health care and research. This existing infrastructure of relationships and resources will facilitate the successful implementation and evaluation of the NCM linkage intervention. Traditional OEF/OIF/OND outreach counselors educate returning Veterans about their VA eligibility, facilitate enrollment and subsequent appointment scheduling. The NCM will have a complementary role in that her interventions will be specific to PTSD and EBP treatment.

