Descriptive statistics will be used to analyze individual items and mean scores on each of the various screens. Estimated power for within group mean differences (i.e., paired t-tests) based on the smaller of the two groups (i.e., N=400: 120 PTSD positive/280 PTSD negative) and assuming a conservative variance=2 and a mean difference of .5, then power=97%. A larger sample size n=280), a smaller observed variance, or a larger observed mean difference would all provide additional power. The power to detect mean differences between groups (120 PTSD positive v. 280 PTSD negative) assuming a conservative variance=2 and a mean difference is calculated to be of .5, then power=90%. Power estimates for differences in proportions are expectedly lower but are estimated to be over 90% to detect medium effect sizes (>.4) and 54% to detect small (>.2) effect sizes. Using nQuery 4.0 for power calculation, we found we can detect a 25% difference in the proportion of women with mental health service use (which can be measured for all participants using VA databases) comparing NCM with existing outreach with 81% power using a simple test of proportions. Using logistic regression for the dependent variable of mental health service use and adjusting for covariates such as comorbid substance abuse, depression, and other post-deployment problems, we estimate that we can detect an odds ratio of 2.3 with 84% power or 2.0 with 76% power for NCM vs existing outreach. Given the appealing and personal nature of the concierge NCM, we believe we will find a large OR of these magnitudes.

OMB Considerations: Our QUERI RRP that serves as the foundation for this CREATE proposal was exempt from OMB review since the survey and collection of information being conducted was in connection with research to prevent a clinical disorder (identified as a basis for exemption under 5 CFR 1320.3). We anticipate that this will be the case with this study as it addresses prevention of chronic PTSD entrenchment and associated mental health or social issues (e.g., depression, substance abuse, marital or family maladjustment). We readily obtained OMB exemption for our HSR&D and DoD funded studies with similar domains in OEF/OIF/OND servicewomen.

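### Mental health care use before assignment is not a named covariate, and the initiation outcomes have no defined set of women who could still initiate

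*Combined protocol and SAP*

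**What the plan says.** All references are to the combined protocol and SAP.

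- **Who is randomised.** Under Random Assignment to Route of VA PTSD EBP Access, "RNG women Veterans who screen positive for PTSD will be randomly assigned by the web interface". The Phase 2 participant criteria concern time since deployment, state and ability to complete a web survey. Current care is neither an exclusion nor a stratification factor.
- **Some will be users already.** The nurse case manager (NCM) "Informs Veteran about routes of access to VA or if already enrolled ways to access PTSD EBP". The post-interface survey will "query those who are PTSD positive and who are not engaged in PTSD EBP and other MH care" about their intentions, which implies that others are engaged. Long-term goal 4 in section 1.0 also refers to current users.
- **Outcomes.** Specific Aim 2 is to "evaluate and test differences in VHA initiation and use for those who screen positive for PTSD". Hypothesis 2.b pairs more use of mental health care with initiation of EBP. The Phase 2 Intervention Process also lists initiation of mental health services among the utilisation data.
- **Analysis.** The Sample Size Analysis and Statistical Plan states "we can detect a 25% difference in the proportion of women with mental health service use", with 81% power by a simple test of proportions. It then describes a logistic model of mental health service use, "adjusting for covariates such as comorbid substance abuse, depression, and other post-deployment problems".
- **Baseline information.** "Phase 2 of the study will involve 5 Steps: 1) Web-based pre-interface survey"; random assignment is step 4. "The web-based pre-screening survey will query prior and current VA utilization". VA records are available for consenting women.

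**The concern.** There are two gaps.

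**Precision.** Use of a service before assignment is usually among the best predictors of its use afterwards. As the outcome is worded, a woman who simply continues VA mental health care counts as a user in either arm, and her event says little about the access route. Conditioning on baseline use takes out that variation. The covariates named are all comorbid problems.

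**Denominator.** Nothing defines initiation relative to assignment, and there is no look-back. A woman in EBP at assignment cannot initiate it, yet the plan does not say whether she stays in the denominator, leaves it, or counts as a success. The same holds for initiation of mental health services. Two analysts could follow the text and report different proportions, and the choice could be made after the data are seen.

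**Working it through.** **Inputs.** At least 120 PTSD-positive women (Sample Size), taken as 60 per arm. A 25-point difference and 81% power (Statistical Plan). Past-year VA mental health use of 7% (Preliminary Work), which covers all surveyed Reserve/National Guard women and not only those PTSD positive. Not given, so assumed: 1:1 allocation, two-sided 5% test, the outreach-arm rate, the share u of randomised women already in VA mental health care, and the fraction c of them who continue (equal in both arms).

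**Step 1: the plan's figure.** With p̄ the mean of the two rates,

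power = Φ{[Δ√n − 1.96√(2p̄(1−p̄))] / √(p₁(1−p₁) + p₂(1−p₂))}.

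At 25% vs 50%, n = 60: Δ√n = 0.25 × 7.746 = 1.936; 1.96 × √0.46875 = 1.342; denominator √0.4375 = 0.661. Power = Φ(0.594/0.661) = Φ(0.899) = 0.816. At 40% vs 65% it is 0.790, and at 50% vs 75% it is 0.816. The stated 81% therefore reproduces, and it fits several outreach rates about equally well.

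**Step 2: gain from baseline use.** Take the 25 points as the overall difference, baseline users included. If the overall rate in an arm is P, the rate among non-users is q = (P − uc)/(1 − u). For u = 0.07, c = 1: (0.25 − 0.07)/0.93 = 0.194 and (0.50 − 0.07)/0.93 = 0.462. Power was simulated with 200,000 trials per row, comparing a pooled two-proportion z test with a Mantel-Haenszel test stratified by baseline use, without continuity correction.

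| Overall rates | Unadjusted | Stratified, c = 100% | c = 90% | c = 80% |
|---|---|---|---|---|
| 25% vs 50% | 0.82 | 0.87 | 0.85 | 0.84 |
| 40% vs 65% | 0.80 | 0.82 | 0.81 | 0.80 |
| 50% vs 75% | 0.82 | 0.835 | 0.83 | 0.82 |

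The gain is about 2 to 5 points at an outreach rate of 25%, and 0 to 2 points at 40% to 50%. With no treatment effect, the stratified test rejected in 4.9% to 5.0% of trials. At 25% vs 50%, a logistic model with only treatment and baseline use gave 0.872, 0.859 and 0.850, so the choice between the two methods hardly matters.

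**Step 3: the initiation denominator.** Let e be the share in EBP at assignment and r the initiation rate among the rest. The reported proportion is r if women already in EBP are left out, r(1 − e) if they stay in as non-initiators, and r(1 − e) + e if they count as successes. The text fits all three, and the documents give no value for e.

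**The case against.** The covariates follow the words such as, inside a power statement. Baseline use is therefore unnamed, not ruled out. The Statistical Plan also says that health care use before the interface will be analysed, though descriptively. Both points stand, and they limit the first gap to a missing prespecification.

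For use, as opposed to initiation, the text already answers the counting question: any use counts, continuing care included. That stands too, and stating it outright would change no analysis.

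The gain was measured against an unadjusted test, while the plan already adjusts for depression, substance abuse and other problems that may be related to earlier care. This stands: the gain over the planned model is unknown and could be smaller. The gain also depends on the outreach rate, which the plan does not give.

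Three stronger readings are tempting, and the documents support none of them.

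- *A reader might infer bias.* Baseline users are randomised like everyone else and are balanced in expectation. The effects are on precision and definition.
- *A reader might infer that the 81% is overstated.* If the 25 points applied only to non-users (25% vs 50%) and 30% of women were continuing users counted as events, the overall difference would be 0.70 × 25 = 17.5 points and power about 0.49. But the plan states the 25 points for the proportion of women overall, and no passage gives a share near 30%.
- *A reader might infer that the passages conflict.* Aim 2 names both initiation and use, and the model addresses use. Initiation is left undefined, which is an omission.

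**Conclusion.** The concern holds in this limited form. VA mental health use before assignment should be a named covariate, and the initiation outcomes need a defined at-risk set. The gain in precision is small to modest: roughly 0 to 5 points of power over an unadjusted test, assuming 7% baseline users, 60 per arm, a two-sided 5% test and 80% to 100% continuation. The 7% is only a guide to the share among PTSD-positive women, and larger gains need shares that the documents do not supply. The denominator gap does not depend on these assumptions. It exists as soon as any randomised woman is already in the care concerned, and it bears on half of Hypothesis 2.b.

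**What to change.** In the Sample Size Analysis and Statistical Plan:

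1. Prespecify VA mental health use before assignment as a covariate in the logistic model of use. Take it from VA records over a stated look-back, supported by the pre-interface survey. Keep all randomised women in this analysis. If nearly all baseline users have the event and the term separates, use a Mantel-Haenszel test stratified by it.
2. Analyse EBP initiation among women not in EBP at assignment, with the same standing that Hypothesis 2.b gives it beside use. A woman in other VA mental health care but not in EBP stays in this set. If initiation of mental health services is reported, apply the same rule to that care.

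**Cost.** A few sentences, plus fewer women in the initiation analyses. At 7% already in mental health care, 60 × 0.93 ≈ 56 per arm remain for mental health initiation, with power 0.79 for 25% vs 50%. Some extra record abstraction may be needed: the pre-survey is described as asking about VA utilisation in general and names no VA mental health or EBP item, and records cover consenting women only.

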### Preliminary Work:

Focus groups for our recent HSR&D funded study of OEF/OIF RNG servicewomen (8 groups, 5 Mid-Western states, N=39). Our qualitative data suggests that women have significant mental health consequences (PTSD, depression, substance abuse) from deployment exposures which further confound their return to relationship and parenting roles. Thematic coding of transcripts revealed that (1) almost all of the participants had received no information regarding their VA eligibility for services or how to access VA services (48 references in 7 of 8

groups), and (2) that post-deployment adjustment, including depression and PTSD symptoms as well as family re-adjustment, was one of the most frequently noted concerns (51 references in all 8 groups). **The majority of our focus group participants didn't know their post-deployment symptoms were treatable mental health conditions that influence readjustment.**

The quantitative findings from the cross-sectional phase of this study (N= 665) indicates that most RNG servicewomen (79%) did not use mental health care in the past year despite mental health problems at rates consistent with other studies, and that RNG women who did use mental health services were more likely to seek mental health care outside of the VA (15%) instead of within (7%). Conversely, most (82%) endorsed the belief that mental health care counseling and services work, and were less likely to think that VA mental health professionals would not understand their problems (9%) than private care mental health professionals (23%). A fourth of participants reported that mental health care would cost them too much money. **Thus, despite their belief that mental health counseling can help them and that VA mental health care providers could better understand their problems, they chose to not seek care or to do so privately** at a financial cost. This incongruity indicates the existence of barriers to access and unaddressed concerns which are not yet adequately understood.

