Findings from our recently completed Mental Health QUERI RRP (N=131) indicated that **RNG servicewomen completing online screening have substantial post-deployment mental health and readjustment concerns.** Nine post-deployment online screens (for PTSD, depression, substance abuse, prescription drug abuse, military sexual trauma (MST), traumatic brain injury (TBI), family readjustment, combat exposures) were implemented. Less than 1% (n=1) of participants screened negatively for all mental health issues and deployment trauma exposures (recognizing the probable selection bias of participation). The maximum number of positive screens by any individual was 8/9. Most (48%) participants had 3-4 positive screens, while 29% had 1-2 positive screens and 22% had more than 4 positive screens. More importantly, using the VA screen for PTSD, **41% screened positive for PTSD.** Most participants (95%) screened positive for combat trauma exposures, half met the VA screening criteria for MST, and 10% the VA screen for TBI. Thus, the mental health care needs of this group are substantial.

**In this study, RNG servicewomen reported our web-based MH screening and tailored educational intervention for post-deployment readjustment provided needed education they felt they otherwise would not have received (48%), decreased MH stigma (32%) and improved access as two-thirds indicated they would subsequently seek MH care (38% VHA and 26% non-VA care).** Participating women endorsed the online interface for improving subsequent access to mental health care. **Almost a third (32%) reported that the tailored information they received reduced their discomfort with seeking care, 38% indicated that they would subsequently seek assessment from a VA provider, and 26% would do so from a non-VA provider.** The online method of education was shown to be a preferred source of information by users. The majority of participants (74%) indicated they preferred to receive VA information through e-mail and 66% routinely use the internet to seek health information. Most (74%) participants would recommend this web-based educational interface to other military women.

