Sampling: Subjects will be selected through the Defense Manpower Data Center (DMDC) with which [name] has a successful working relationship. Our previous work, on which this study builds, used military e-mail as the sole method of contact. We learned several lessons: (1) RNG servicewomen only sporadically checked their military e-mails which was problematic for recruitment; (2) feedback from participants told us that e-mailing a traditional IRB study invitation and informed consent (6-7 pages) was a participation deterrent; (3) we were unable to follow up with non-responders and determine a true response rate because our original QUERI sampling specifications to DMDC did not request additional information. Consequently, we have revised our protocol for recruiting: (1) we have increased the recruitment and follow-up duration; (2) we have worked with our IRB and Pharos Innovations (developer of the web-based program) to streamline the subject information and consent process; and (3) we have thus revised our DMDC registry requirements to sample potential participants with both e-mail and postal mail. Our respondents will be contacted initially by postal mail with study materials and web-based study link and notification that an e-mail is being mailed the same week for their convenience. Non-responders will be re-contacted in 10 days following initial mailing. DMDC is able to provide sociodemographic and military information (e.g. age, marital status, race, rank, number of deployments) that will subsequently allow us to compare study participants with refusals and non-responders. This will facilitate follow up and better analysis of the generalizability of findings. Web-based interface participants will be reimbursed \$30.00 for their participation.

Sample Size: Taking into account a conservatively estimated e-mail only response rate (15%) and response rates based on letter contact and phone follow-up (48% - 70%), we conservatively estimate a 20% response rate using e-mail and letter recruitment and therefore will request a sample of 2,000 women from DMDC to achieve a final sample size of 400. Assuming conservatively that 30% of the sample will screen positively for PTSD (45% of RNG women participating in our original QUERI web-based screen met criteria for PTSD), this will allow us to have at least 120 women with a positive screen for PTSD.

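### With 120 randomised women, power for nurse case manager versus outreach is at most about 47% at OR 2.0 and 62% at OR 2.3, not the stated 76% and 84%

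*Combined protocol and SAP*

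**What the plan says.** Under Random Assignment to Route of VA PTSD EBP Access, "RNG women Veterans who screen positive for PTSD will be randomly assigned by the web interface to one of two conditions": the study nurse case manager (NCM) or existing outreach. Under Sample Size in Phase 2, 2,000 invitations, a 20% response and a 30% positive screen lead to the statement that "this will allow us to have at least 120 women with a positive screen for PTSD".

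The power statements are in Sample Size Analysis and Statistical Plan. For the unadjusted comparison, "we found we can detect a 25% difference in the proportion of women with mental health service use", "comparing NCM with existing outreach with 81% power using a simple test of proportions". For a logistic regression of mental health service use adjusted for comorbid conditions, "we estimate that we can detect an odds ratio of 2.3 with 84% power or 2.0 with 76% power for NCM vs existing outreach". The paragraph closes with the expectation that "we believe we will find a large OR of these magnitudes".

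The section gives no control-arm rate, significance level, sidedness or allocation ratio for these calculations.

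**The concern.** The three power figures concern the same comparison and, as far as the plan shows, the same women. A 25-point difference is a larger effect than an OR of 2.3 at any control rate, yet the OR of 2.3 is given the higher power.

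NCM versus outreach is the only randomised comparison and the test of Hypothesis 2.b. If the OR figures are too high, the study is presented as well powered for effects that it would miss about as often as not. A null result could then be misread as evidence against the NCM.

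**Working it through.** **Inputs.** Randomised women: 2,000 × 0.20 × 0.30 = 120 (Sample Size; the power section repeats 120 PTSD positive). Not stated, so assumed: 1:1 allocation (60 per arm), two-sided 5%, and no loss, because the plan measures this outcome in VA databases. Of the splits tried, 1:1 gives the highest power. The control rate is not stated and was scanned from 1% to 95%.

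**Formula.** For control rate p1 and NCM rate p2, with d = p2 − p1, p̄ = (p1 + p2)/2 and n per arm:

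power = Φ[(d − 1.96·s0)/s1], s0 = √(2p̄(1−p̄)/n), s1 = √([p1(1−p1) + p2(1−p2)]/n)

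For a given OR, p2 = OR·p1/(1 − p1 + OR·p1).

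**1. The plan's own 81%.** With 25% versus 50%, s0 = 0.0884 and s1 = 0.0854. Then (0.25 − 1.96 × 0.0884)/0.0854 = 0.90, so power is 81.6%. It is also 81.6% for 50% versus 75%, and 78.9% at the least favourable control rate (37.5%). The 81% reproduces. Two-sided 5% also reproduces the 97% (paired, 120 women) and 90% (120 versus 280) in the same paragraph.

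**2. The two OR figures, same set-up.**
- OR 2.0, control 41%: p2 = 58.2%, d = 0.1716, s0 = 0.0913, s1 = 0.0899. (0.1716 − 0.1789)/0.0899 = −0.08, so power is 46.7%. This is the maximum over control rates.
- OR 2.3, control 40%: p2 = 60.5%, d = 0.2053, s0 = 0.0913, s1 = 0.0893. (0.2053 − 0.1789)/0.0893 = 0.295, so power is 61.6%. This is again the maximum.

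| Control rate | OR 2.0 (stated 76%) | OR 2.3 (stated 84%) |
|---|---|---|
| 7% | 19.6% | 27.4% |
| 25% | 41.7% | 56.6% |
| about 40% (maximum) | 46.7% | 61.6% |
| 50% | 45.6% | 59.7% |

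The 7% is past-year VA mental health use in the earlier survey (Preliminary Work). It covers all surveyed women, so it is illustrative only. Other tests give similar maxima: Wald 46.4% and 60.7%; exact chi-square 48.7% and 63.5%.

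**3. Internal contradiction.** The largest risk difference for a given OR is (√OR − 1)/(√OR + 1): 17.2 points at OR 2.0 and 20.5 points at OR 2.3. The smallest OR for a 25-point difference is (0.625/0.375)² = 2.78. In the same women at the same control rate, the smaller effect cannot have the higher power.

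**4. The pair does not fit itself.** For a two-arm comparison, a sample size that gives 76% at OR 2.0 gives 87% to 91% at OR 2.3 (control rates 7% to 85%), not 84%.

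**5. Other assumptions.** At the pilot screen-positive rates, 41% (Preliminary Work) gives 400 × 0.41 = 164 women and 45% (Sample Size) gives 400 × 0.45 = 180.

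| Set-up | Maximum, OR 2.0 | Maximum, OR 2.3 | 25-point power, at least |
|---|---|---|---|
| One-sided 5%, 120 women | 59% | 73% | 87% |
| Two-sided, 164 women | 60% | 75% | 90% |
| Two-sided, 180 women | 64% | 79% | 92% |
| One-sided, 164 women | 71% | 84% | 95% |
| One-sided, 180 women | 75% | 87% | 96% |
| Plan | 76% | 84% | 81% |

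No row gives the plan's three figures together.

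**6. Covariate adjustment.** For a conditional OR under 1:1 allocation, the information on the arm coefficient cannot exceed N × ¼ × ¼ = 120/16 = 7.5. Power is then at most Φ(ln OR × √7.5 − 1.96): Φ(1.898 − 1.96) = 47.5% at OR 2.0 and Φ(2.281 − 1.96) = 62.6% at OR 2.3. Simulated logistic regressions (120 women, two binary covariates of 50% prevalence with ORs of 1.5 to 5, baseline odds set at 40%, 4,000 runs per setting) gave 38% to 46% and 52% to 60%.

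**7. What the stated power would need.** At the most favourable control rate: 120 per arm for 76% at OR 2.0, and 103 per arm for 84% at OR 2.3. With 60 per arm, the smallest OR with 80% power is about 2.8 to 2.9 for control rates of 25% to 50%, 3.9 at 10% and 4.6 at 7%.

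**The case against.** The best defence is that the OR figures rest on unstated assumptions. The plan says at least 120 women, and its pilot found a higher screen-positive rate. One-sided testing with 180 women gives 75% and 87%, close to the stated pair. But the 25-point power would then be at least 96%, so this route works only if the two adjacent sentences used different sample sizes or sidedness. Nothing in the plan says so.

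Some limits on the criticism stand:
- The 47% and 62% depend on the test by 1 to 2 points, so they should be read as approximate.
- The 7% control rate does not fit the plan's 81%: a 25-point difference from 7% has about 94% power with 60 per arm. In the pilot, 38% said they would seek a VA assessment, so true use in PTSD-positive women may be well above 7%.
- The 25-point figure is marginal and the ORs are covariate-adjusted. The information bound in step 6 deals with the adjusted OR directly and gives the same answer.
- The 120 was set from response and screening rates, not from the ORs, so correcting the ORs does not undo the sample size derivation.

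The stated pair may come from a logistic regression formula for a normally distributed covariate. With 120 women and an event rate of 20% to 21%, that formula gives about 74% to 76% at OR 2.0 per standard deviation and 85% to 86% at OR 2.3. This is inference, not something the plan states. The formula does not apply to a two-level treatment arm.

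**Conclusion.** The concern holds. With 120 women, 1:1 allocation and two-sided 5%, power is at most about 47% at OR 2.0 and 62% at OR 2.3, which is 29 and 22 points below the stated values. The chance of missing a true effect is about 53% and 38%, against the implied 24% and 16%; by exact chi-square it is about 51% and 37%. It is higher if the control rate is far from 40%.

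The size of the gap rests on assumptions that the plan leaves unstated. The contradiction between 81% for 25 points and 84% for OR 2.3 needs only the same women, the same control rate and the same test conditions. The 81% itself is sound for control rates of about 25% to 50%. The two OR figures should be corrected before the plan is relied on.

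**What to change.** In Sample Size Analysis and Statistical Plan:

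1. State the assumed control-arm rate of VA mental health use and its basis in PTSD-positive women, together with alpha, sidedness and allocation.
2. Replace the OR sentence with the power at that control rate. For 60 per arm and two-sided 5%, at OR 2.0 and OR 2.3, this is 42% and 57% at a 25% control rate and 46% and 60% at 50%. Note that 47% and 62% are approximate ceilings. If a low-use scenario is shown, 7% gives 20% and 27%; say that the 7% comes from all surveyed women.
3. Add the smallest OR detectable with 80% power: about 2.8 to 2.9 for control rates of 25% to 50%, and about 4.6 at 7%.
4. Delete the closing expectation about the size of the OR, or tie it to that detectable OR and give its basis.

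The cost is wording only. No participants are added and the design does not change, but the stated power becomes less favourable.
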